4.5.3. Vital Signs

Descriptive statistics of the highest and lowest values at each visit and the highest and lowest value at any post-baseline visit (including unscheduled post-baseline measurements) will be summarized by study drug group for each vital sign parameter (heart rate, blood pressure, respiratory rate, and temperature).

The change from baseline to the highest and lowest values at each post-baseline visit and the highest and lowest value at any post-baseline visit (including unscheduled post-baseline measurements) will be provided for each vital sign parameter by treatment group. Change from baseline to the highest and lowest values at each post-baseline visit will be calculated for each subject and parameter as the highest or lowest value at the specified visit minus the baseline highest or lowest value. If multiple values are obtained during the Screening period, the last non-missing values collected prior to the first dose of study drug will be used for the baseline.

A summary of potentially clinically significant (PCS) values, identified as values meeting both the criterion value and the change from baseline criterion listed in **Table 4-3**, will be provided for the worst post-baseline value (which includes unscheduled post-baseline measurements). The incidence of PCS values will be summarized by treatment group for the worst post-baseline value and will be listed and flagged in by-subject listings.

For all analyses of temperature, temperatures obtained by non-oral methods of rectal or tympanic will be converted to oral temperatures by subtracting 0.3 °C from the temperature in °C. Temperatures obtained by temporal methods will be converted to oral temperatures by adding 0.3°C to the temperature in °C.

A by-subject listing of vital signs reported at each visit will be provided.

Table 4-3: Criteria for Potentially Clinically Significant Vital Signs

Vital Sign Parameter	Flag	Criterion Value	Change from Baseline
Systolic Blood Pressure (mm Hg)	High (CH)	≥ 180 mmHg	Increase of ≥ 20 mmHg
	Low (CL)	≤ 90 mmHg	Decrease of ≥ 20 mmHg
Diastolic Blood Pressure (mm Hg)	High (CH)	≥ 105 mmHg	Increase of ≥ 15 mmHg
	Low (CL)	≤ 50 mmHg	Decrease of ≥ 15 mmHg
Heart Rate (bpm)	High (CH)	≥ 120 bpm	Increase of ≥ 15 bpm

Vital Sign Parameter	Flag	Criterion Value	Change from Baseline
	Low (CL)	≤50 bpm	Decrease of ≥15 bpm
Temperature (°C)	High (CH)	>38°C	Increase of ≥1°C
	Low (CL)	≤36 °C	Decrease of ≥1°C
Respiratory Rate (breaths/minute)	High (CH)	≥30 breaths/minute	Increase of ≥10 breaths/minute
	Low (CL)	≤8 breaths/minute	Decrease of ≥4 breaths/minute

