7.1.2 Systemic Signs of Candidemia and Invasive Candidiasis

It is a requirement that at least 1 systemic sign attributable to candidemia and/or invasive candidiasis be present at Screening for the subject to be eligible for enrollment. The Screening period for assessing systemic signs for inclusion in the study may include the 12 hours prior to the collection of the qualifying positive culture when systemic signs of infection were the reason for specimen collection (blood culture or fluid from a sterile site culture or qualifying rapid IVD [e.g., T2Candida Panel]) through study randomization. The possible signs of infection that might be attributable to candidemia and/or invasive candidiasis at baseline include fever, hypothermia,

hypotension, tachycardia, tachypnea, and local signs of inflammation (erythema, edema, heat, and pain at the site of the qualifying blood culture).

For the listed systemic signs of candidemia, the qualifying parameters are provided below:

Systemic Sign of Candidemia	Qualifying Parameters
Fever	Oral or axillary temperature $\geq 38^{\circ}\text{C}$ (100.4°F) or a tympanic, temporal, rectal, or core body temperature $\geq 38.3^{\circ}\text{C}$ (101°F)
Hypothermia	Tympanic, temporal, rectal, or core body temperature $\leq 35^{\circ}\text{C}$ (95.2°F)
Hypotension	Systolic blood pressure < 90 mm Hg or mean arterial pressure < 70 mm Hg with a normovolemic or hypervolemic status
Tachycardia	Heart rate > 100 beats per minute with a normovolemic or hypervolemic status
Tachypnea	Respiratory rate > 20 breaths per minute
Local Signs of Inflammation	Erythema (rubor), edema (tumor), heat (calor), and pain (dolor) at the site of infection

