2.3. Exploratory Efficacy Outcomes

2.3.1. Resolution of Attributable Systemic Signs of Candidemia and/or Invasive Candidiasis that were Present at Baseline

It is a requirement that at least 1 systemic sign attributable to candidemia and/or IC be present at Screening for the subject to be eligible for enrollment. The Screening period for assessing systemic signs for inclusion in the study may include the 12 hours prior to the drawing of the qualifying positive culture (when systemic signs of infection resulted in obtaining blood cultures), qualifying positive culture from a sterile site, or qualifying rapid in vitro diagnostic, through enrollment. The possible signs of infection that might be attributable to candidemia and/or IC at baseline include fever, hypothermia, hypotension, tachycardia, tachypnea, and local signs of inflammation.

For the listed systemic signs of candidemia, the qualifying parameters are listed below:

Fever: Oral or axillary temperature $\geq 38^{\circ}\text{C}$ [100.4°F] or a tympanic, temporal, rectal, or core body temperature $\geq 38.3^{\circ}\text{C}$ [101°F]

Hypothermia: Tympanic, temporal, rectal, or core body temperature $\leq 35^{\circ}\text{C}$ [95.2°F]

Hypotension: Systolic blood pressure < 90 mmHg or mean arterial pressure < 70 mmHg with a normovolemic or hypervolemic status

Tachycardia: Heart rate > 100 beats per minute with a normovolemic or hypervolemic status

Tachypnea: Respiratory rate > 20 breaths per minute

Local signs of inflammation: Erythema, edema, heat and pain at the site of the qualifying culture

Resolutions of systemic signs will be programmatically categorized as follows:

- Yes (resolution): Resolution of all attributable systemic signs of candidemia and/or invasive candidiasis that were present at baseline and no new attributable systemic signs that were not present at baseline
- No (not resolved): New attributable systemic signs that were not present at baseline or lack of resolution of any attributable systemic signs of candidemia and/or invasive candidiasis that were present at baseline

Subjects whose assessment of systemic signs was not completed at a visit or at baseline for any reason (including death) will not be included in the analysis.

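### SAP 4.5.3 adds 0.3°C to temporal temperatures, whereas the fever criterion in SAP 2.3.1 and protocol 7.1.2 implies subtracting 0.3°C; core readings have no stated rule

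*SAP*

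**What the plan says.** Two parts of the plan relate non-oral temperatures to oral ones.

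- **Fever criterion.** Protocol 7.1.2 sets fever at 38.0°C or more for oral or axillary readings, and at 38.3°C or more for a "tympanic, temporal, rectal, or core body temperature". SAP 2.3.1 repeats this with the same grouping ("a tympanic, temporal, rectal, or core body temperature") and the same two cut-offs.
- **Conversion for vital signs.** SAP 4.5.3 states that "temperatures obtained by non-oral methods of rectal or tympanic will be converted to oral temperatures by subtracting 0.3 °C from the temperature in °C". It then says: "Temperatures obtained by temporal methods will be converted to oral temperatures by adding 0.3°C to the temperature in °C". The rule covers every temperature analysis in that section. Core is not mentioned, although the vital-sign footnotes to protocol Table 1 and SAP Appendix 2 list it as a recorded method.

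Table 4-3 of the SAP then applies the PCS criteria. PCS-high needs a value above 38°C and an increase from baseline of at least 1°C. PCS-low needs a value of 36°C or less and a decrease of at least 1°C. Both parts must be met, and the summary uses the worst post-baseline value, unscheduled readings included.

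**The concern.** The fever criterion treats a temporal reading as sitting 0.3°C above oral, like rectal and tympanic. The conversion rule treats it as sitting 0.3°C below oral. Neither document explains why temporal should be handled in opposite directions. Because SAP 2.3.1 carries the fever criterion, the SAP disagrees with itself as well as with the protocol.

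At stake are the descriptive temperature summaries and the PCS counts by arm. A subject could be listed with a PCS-high temperature on a reading that is not fever by the plan's own definition. Where the measurement method changes between baseline and a later visit, part of the calculated change would come from the conversion and not from the patient. Where methods are mixed, the offset could also alter which reading is taken as the worst.

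**Working it through.** **Inputs.** Fever cut-offs: 38.0°C oral or axillary; 38.3°C tympanic, temporal, rectal or core (protocol 7.1.2, SAP 2.3.1). Conversions: −0.3°C rectal and tympanic, +0.3°C temporal, none stated for core (SAP 4.5.3). PCS-high: >38°C and a rise of at least 1°C (SAP Table 4-3).

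**Step 1: the offset implied by the fever criterion.** Implied offset to oral = 38.0 − 38.3 = −0.3°C for all four non-oral, non-axillary methods. For rectal and tympanic, SAP 4.5.3 reproduces this exactly. For temporal, the difference is (+0.3) − (−0.3) = 0.6°C.

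**Step 2: method by method, readings to one decimal (°C).**

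| Method | Fever cut-off | Implied offset | SAP 4.5.3 offset | Raw reading mapped to oral 38.0 | Below fever cut-off but >38 after SAP rule |
|---|---|---|---|---|---|
| Oral, axillary | 38.0 | 0 | none stated | 38.0 | none |
| Rectal, tympanic | 38.3 | −0.3 | −0.3 | 38.3 | none |
| Temporal | 38.3 | −0.3 | +0.3 | 37.7 | 37.8 to 38.2 |
| Core, if left as read | 38.3 | −0.3 | not stated | 38.0 | 38.1 to 38.2 |

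Leaving axillary readings as they are agrees with the fever criterion, so the missing rule there does no harm.

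**Step 3: the full two-part flag, temporal at both times.** The offset cancels in the change, so only the >38°C part is affected.

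- 36.8 then 37.8 becomes 37.1 then 38.1; rise 1.0; flagged PCS-high, yet 37.8 is below 38.3 and is not fever.
- 37.5 then 37.8 becomes 37.8 then 38.1; rise 0.3; not flagged.

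**Step 4: method changes between baseline and follow-up.** Take R rectal or tympanic at baseline and T temporal later.

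- SAP rule: (T + 0.3) − (R − 0.3) = T − R + 0.6.
- Implied offsets: (T − 0.3) − (R − 0.3) = T − R.

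The shift is +0.6°C, or −0.6°C if the order is reversed, against a 1°C criterion. With rectal 37.0 then temporal 37.8, the SAP rule gives 36.7 then 38.1, change 1.4, flagged. The implied offsets give 36.7 then 37.5, change 0.8, not flagged. If core is left as read at baseline, the SAP change to temporal is (T + 0.3) − C against T − C, a shift of 0.3°C.

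**Step 5: after alignment.** With −0.3°C for temporal and core, both map 38.3 to 38.0 and the bands in the last column of the table disappear. One boundary value remains: a raw 38.3 meets the fever rule (at least) but not PCS-high (greater than). Rectal and tympanic already have that mismatch at 38.3, and oral and axillary at 38.0.

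**The case against.** The strongest reply is that the fever list gives entry cut-offs, not conversion formulas, so the −0.3°C for temporal is inferred. That is fair, and it limits the argument at the low end. The hypothermia cut-off (35°C or less) applies to tympanic, temporal, rectal and core with no oral counterpart, so it implies no offset. A reader might infer a low-temperature conflict as well, for example because temporal 35.8 becomes 36.1 and escapes the PCS-low value. But 35.8 is not hypothermia under the protocol either, so neither rule picks it out and no contradiction is shown.

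It is also true that the PCS and systemic-sign thresholds were never a matched set: heart rate is 120 or more against above 100, respiratory rate 30 or more against above 20, and low temperature 36 or less against 35 or less. A reading that crosses one cut-off and not the other is not in itself an error. What survives is narrower: the sign of the temporal conversion. The SAP's own rectal and tympanic conversion matches the fever offset exactly, and only temporal is reversed.

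A reader might also infer that fever at entry, sign resolution or clinical cure would be affected. The documents do not support that. The fever criterion has its own method-specific cut-offs, attribution of signs is the investigator's determination (SAP 4.1.6), clinical cure is investigator-assessed, and nothing in SAP 4.5.3 feeds either primary endpoint. Nor should every temporal reading of 37.8 to 38.2 be called flagged, because the 1°C change is also required. Finally, core is a gap: the SAP states no rule for it, and does not say that core readings stay unconverted.

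**Conclusion.** The point holds as a minor but definite inconsistency. Two stated rules place temporal readings on oral scales 0.6°C apart, and one recorded method has no rule. Temporal readings of 37.8 to 38.2°C meet the PCS-high value while below the fever cut-off, and mixed-method changes move by up to 0.6°C against a 1°C criterion. The practical effect depends on how many readings are temporal or core and how often the method changes, which the documents do not give. The effect is confined to descriptive temperature summaries and PCS counts; sample size, alpha and the primary endpoints are untouched. The conclusion assumes that the two fever cut-offs express an oral equivalence. The documents do not show which temporal direction is correct, only that both cannot serve as one oral scale.

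**What to change.** Before unblinding, amend SAP 4.5.3 so that one oral equivalence is used throughout. The simplest way is to extend the offset implied by the SAP's own fever criterion: subtract 0.3°C for temporal and core as well as rectal and tympanic, and leave oral and axillary as read. If the sponsor has reason to treat temporal differently, the SAP should give that reason and report the PCS temperature counts under both offsets. In either case, state the rule for core. PCS counts at both the high and the low end will move with the change.

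The cost is one or two sentences in the SAP and a small programming change, with no new data. The protocol's fever cut-off should not be altered to fit: it supports an inclusion criterion, and randomization for primary enrollment closed on 16 August 2021 (SAP 1.2.2), before SAP V4.0 of 2 November 2021.

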4.5.4. Electrocardiogram

Descriptive statistics of ECG parameters will be presented by treatment group and will include change from baseline. If multiple values are obtained during the Screening period, the last non-missing values collected prior to the first dose of treatment will be used for the baseline. QTcF is calculated using the formula: $QTcF = QT \text{ (msec)} / (RR \text{ in seconds})^{1/3}$ where RR (sec) can be calculated from 60 divided by Heart rate (bpm). The number and percentage of subjects with the change from baseline QTcF ≥ 30 msec and ≥ 60 msec will be presented.

A by-subject listing of ECG parameters reported at each visit will be provided.

4.5.5. Physical and Retinal Examinations

Physical exam findings from Screening, Day 14 (± 1), Day 30 (± 2), End of Treatment (≤ 2 days of last dose), the Follow-up visit and unscheduled visits will be presented in a by-subject listing. Abnormal findings from retinal examinations and whether or not the subject had evidence of candida endophthalmitis or chorioretinitis will be provided in a by-subject listing. Signs and symptoms of tremor, ataxia and peripheral neuropathy determined from neurological examinations at Screening, End of Treatment (≤ 2 days of last dose) and unscheduled visits will be presented in a by-subject listing.

4.5.6. Neurological Questionnaires

Assessments of Chemotherapy-Induced Peripheral Neuropathy questionnaire (QLQ-CIPN20 version 3.0) and Scale for the Assessment and Rating of Ataxia (SARA, version date 13 Jun 2006) were conducted on patients enrolled prior to Protocol Amendment 3. Results from these two neurological questionnaires will be presented in by-subject listings.

4.6. PK Sampling

Blood samples will be collected from all subjects receiving study drug, although only PK samples from subjects receiving Rezafungin for Injection will be analyzed. Bioanalytical analysis will be performed by an independent, central bioanalytical laboratory using a validated assay.

Only samples taken within the timepoint windows will be included in summary statistics and evaluations of safety and efficacy by PK tertiles described below.

Timepoint windows are defined as follows:

- Day 1, 10 Minutes before end of infusion (EOI): between 15 minutes prior to EOI and 5 minutes after EOI.
- Day 1, Between EOI and 12 Hours after EOI: between 5 minutes prior to EOI to 15 hours after EOI.
- DAY 2, 3, 4, or 5 Random Draw: any time
- DAY 8 PRE-DOSE: within 30 minutes prior to Day 8 infusion start
- DAY 14: any time.
- DAY 15 PRE-DOSE: any time on Day 15 prior to Day 15 infusion start
- DAY 22 PRE-DOSE: any time on Day 22 prior to Day 22 infusion start

Summary statistics (number of subjects, arithmetic mean, SD, coefficient of variation (CV%), median, minimum, maximum, tertiles, and geometric mean of plasma concentration) will be provided for the PK Population by timepoint mentioned above.

Timing of pharmacokinetic samples will be presented in a by-subject listing.

The FDA and EMA primary endpoints of all-cause mortality and global response, respectively, will be summarized by upper, mid, and lower tertiles of plasma concentration on Day 1 (10 minutes before the end of infusion) and on Day 8 (pre-dose) in the PK Population.

[figure not shown]
The number and percentage of any TEAE in the rezafungin group and any TEAEs occurring in >40% (by SOC and PT) will be summarized by upper, mid, and lower tertiles of plasma concentration on Day 1 (10 minutes before the end of infusion) and on Day 8 (pre-dose) in the PK Population

The following rules will be applied prior to summarizing if plasma concentration values that are below the limit of quantification (BLQ), or missing (e.g., no result [NR]):

[figure not shown]
- BLQ or NR values will be set to missing for summary purposes. Values that are BLQ will be displayed as “BLQ” in listings.
- If there are fewer than 3 values in the data series, only the minimum, maximum and n will be presented. The other summary statistics will be denoted as not calculated (NC).

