7.4.2 Early Discontinuation from Study Drug Administration

For subjects who prematurely discontinue study drug (i.e., before the anticipated full course of study drug therapy required for effective treatment of candidemia and/or invasive candidiasis), EOT assessments should be performed on the day of discontinuation. For premature study drug discontinuation, Day 14 efficacy assessments should also be performed at EOT, except when the subject is believed to be a clinical cure, then the efficacy assessments should still be performed at the Day 14 visit to ensure there is no relapse between EOT and Day 14. All safety assessments and assessment of mortality should be done for subjects who discontinue study drug early. The reason for premature discontinuation of study drug administration should be recorded on the appropriate page(s) of the eCRF. Reasons for withdrawal from study drug may include, but are not limited to:

- Cultures negative for *Candida* spp.
 - Blood culture is positive for yeast at enrollment, but the final local blood culture results conclude the yeast is not *Candida* spp.
 - Subject is enrolled based on a rapid IVD test positive for *Candida* spp., but final local blood culture results from Screening or tissue/fluid culture results from a normally sterile site are negative for *Candida* spp. (withdrawal not required but based on the Investigator's discretion)

- Safety
 - Subject unable or unwilling to continue or informed consent withdrawn
 - Occurrence of an AE that, in the opinion of the Investigator, warrants the subject's permanent discontinuation from study drug therapy. This includes development of a clinically significant laboratory abnormality that requires discontinuation from study drug (IV and IV/oral) therapy. In the event of discontinuation from study drug therapy due to the occurrence of an AE, the study site should notify the Medical Monitor as soon as possible
 - Suspected or confirmed pregnancy or nursing during the study drug administration period
- Excluded types of invasive candidiasis

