13.1 Analysis Populations

The analysis populations are defined for this study as follows:

- The intent-to-treat (ITT) population will include all randomized subjects, regardless of whether the subject receives study drug.
- The Safety population will include all subjects who received any amount of study drug.
- The mITT population will include all subjects who had documented *Candida* infection based on Central Laboratory evaluation of a culture from blood or another normally sterile site obtained ≤ 4 days (96 hours) before randomization and received ≥ 1 dose of study drug.
- The clinically evaluable (CE) population will include all subjects in the mITT population who also met inclusion criterion #4, did not meet exclusion criteria #1, #2, or #5, had an assessment of both mycological and clinical response at Day 14 in the window of Day 14 (± 1 day) (subjects with invasive candidiasis documented by radiologic/imaging evidence also must have an assessment of radiologic response), and did not have any other factor that could confound the assessment of the global response at Day 14.
- PK Analysis Population will include all Rezafungin for Injection subjects with at least 1 plasma sample obtained for PK analysis.

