2.1.1. Estimand Framework

An addendum to ICH E9 introduces the concept of an estimand which translates the trial objective into a precise definition of the treatment effect that is to be estimated. The description of the estimand includes four attributes: the population, the variable (or endpoint) to be obtained for each patient, the specification of how to account for intercurrent events (ICE), and the population-level summary for the variable. These attributes are described below for the FDA and EMA primary efficacy outcomes.

Table 2-1: Estimand Attributes

	ACM at Day 30 (FDA)	Global Response at Day 14 (EMA)
Population	mITT Population (see Section 2.6)	mITT Population (see Section 2.6)
Variable/Endpoint	Deceased by Day 30	DRC global response of cure
Handling of intercurrent events	Treatment policy estimand as measured irrespective of any ICE 
 • Missing data considered deceased 	Composite estimand as the following ICE's are incorporated into the variable/endpoint: 
 • Death (failure) • Receipt of rescue therapy (failure) • Discontinuation of study drug due to an adverse event (failure) • Missing data (classified as indeterminate but analyzed as a failure)
Population-level summary	Difference between treatment groups in percentage of subjects who died	Difference between treatment groups in percentage of subjects with a DRC global response of cure

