2.6. Population Definitions

The following analysis populations will be evaluated and used for presentation and analysis of the data:

- The intent-to-treat (ITT) population will include all randomized subjects.
- The safety population will include all subjects who received any amount of the study drug. Safety assessments will be performed on the safety population. Subjects who receive the wrong study drug for their entire course of study drug will be analyzed in the treatment group based on the drug received. Subjects who receive the wrong study drug for part of their course of study drug will be analyzed in the treatment group based on majority of (i.e., most frequent) doses received.
- The mITT population will include all subjects who had a documented *Candida* infection based on Central Laboratory evaluation of a blood culture or a culture from a normally

sterile site obtained ≤ 4 days (96 hours) before randomization and received ≥ 1 dose of study drug.

- The clinically evaluable (CE) population will include all subjects in the mITT population who also met inclusion criterion #4, did not meet exclusion criteria #1, #2, and #5, had a response other than indeterminate for both mycological and clinical response as assessed by DRC at Day 14 in the protocol specified window of Day 14 \pm 1 day (subjects with invasive candidiasis documented by radiologic/imaging evidence also must have a radiological response by DRC other than indeterminate), and did not receive a concomitant antifungal that could confound the assessment of the global response at Day 14.
- The Pharmacokinetic (PK) population will include all subjects who received any amount of study drug and have at least one blood sample with measurable concentrations.

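### SAP 4.6 tabulates global response by concentration tertile in the PK Population, where a subject without a positive baseline Candida culture is counted but cannot be a cure

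*SAP*

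**What the plan says.** SAP 4.6 (PK Sampling) sets out the exposure tables: "The FDA and EMA primary endpoints of all-cause mortality and global response, respectively, will be summarized by upper, mid, and lower tertiles" of plasma concentration. The timepoints and analysis set follow: "10 minutes before the end of infusion) and on Day 8 (pre-dose) in the PK Population", the first of these being on Day 1.

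SAP 2.6 defines that set: "The Pharmacokinetic (PK) population will include all subjects who received any amount of study drug and have at least one blood sample with measurable concentrations". Protocol 13.1 words it differently, but also without a culture requirement: "PK Analysis Population will include all Rezafungin for Injection subjects with at least 1 plasma sample obtained for PK analysis".

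The efficacy population is stricter. SAP 2.6: "The mITT population will include all subjects who had a documented *Candida* infection based on Central Laboratory evaluation" of a culture taken within 96 hours before randomization, plus at least one dose. SAP Table 2-1 assigns both primary estimands to mITT. SAP 4.3 makes mITT the default for efficacy unless another set is stated, and 4.6 states another set.

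The protocol foresees dosed subjects without a positive Candida culture. Protocol 7.4.2 lists, among the reasons for stopping study drug: "Blood culture is positive for yeast at enrollment, but the final local blood culture results conclude the yeast is not" Candida. It also lists entry on a positive rapid test followed by negative cultures, where withdrawal is left to the investigator. Protocol 7.1.1 says that a subject may enter on a rapid test, but that a positive Candida culture remains the required objective measure in the efficacy analyses.

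**The concern.** The global response table applies an outcome to subjects for whom its best category is not defined. A subject with no positive baseline culture sits in a tertile's denominator and, by definition, never in its numerator, whatever the concentration. This lowers the cure rate shown. It can also tilt the comparison across tertiles if such subjects are spread unevenly. No rule in the SAP says how to classify them.

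What is at stake is the reading of the only tables in the SAP that set rezafungin concentration against the two primary endpoints. Their cure rates could sit below the mITT rate for reasons unrelated to exposure.

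**Working it through.** **Definitions side by side**

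1. Entry to the table (SAP 4.6 with 2.6): a dose and a measurable concentration. No culture is needed.
2. Eradication (SAP Table 2-3): one route requires a positive baseline blood culture, the other a positive baseline culture from a normally sterile site. Presumed eradication belongs to the second route.
3. Global cure (SAP Table 2-2): requires eradication or presumed eradication together with clinical cure and, where applicable, radiological cure.
4. Denominator (SAP 2.2.1): everyone in the specified analysis population.

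From 1 to 4, a subject with no positive baseline culture is counted and cannot be a cure. Failure stays reachable, for example through death or a change of antifungal therapy.

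**The plan's own figures**

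Inputs (Protocol 13.8): cure 70% in both arms, margin 20%, one-sided alpha 0.025, power 80%, continuity-corrected Z, 85% evaluable.

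- Uncorrected: n = 2 × 0.70 × 0.30 × (1.960 + 0.842)² / 0.20² = 82.4 per arm.
- Corrected: (82.4/4) × [1 + √(1 + 4/(82.4 × 0.20))]² = 92.1 per arm. The plan states 92.
- Randomized: 184/0.85 = 216.5. The plan states approximately 218.

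The planned sizes reproduce.

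**How many subjects could be affected**

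- Rezafungin arm: 218/2 = 109 randomized, 92 planned in mITT, so 109 − 92 = 17 outside it.
- The documents do not say how many of these 17 are dosed and have a measurable concentration. The assumed range is 0 to 17.

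**Effect on the displayed cure rate**

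Assume 70% cure in mITT (0.70 × 92 = 64.4 cures), all 92 mITT subjects in the table, and k further PK subjects, none of whom can be a cure. Displayed rate = 64.4/(92 + k).

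| k | Subjects in table | Cure rate shown |
|---|---|---|
| 0 | 92 | 70.0% |
| 5 | 97 | 66.4% |
| 10 | 102 | 63.1% |
| 17 | 109 | 59.1% |

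**Effect across tertiles (illustration only)**

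Take k = 17, tertiles of 36, 37 and 36, and no exposure effect.

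- Spread 6/6/5: 0.70 × 30/36 = 58.3%, 0.70 × 31/37 = 58.6%, 0.70 × 31/36 = 60.3%.
- Spread 9/5/3: 0.70 × 27/36 = 52.5%, 0.70 × 32/37 = 60.5%, 0.70 × 33/36 = 64.2%.

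For scale, the 95% half-width for a difference between two tertiles of 36 at 70% cure is 1.96 × √(2 × 0.70 × 0.30/36) = 21 points. The 11.7-point gap in the uneven case is smaller than that.

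**The case against.** The strongest reply is that the tables are descriptive. SAP 4.6 specifies no test or interval for them, and nothing in them reaches the non-inferiority comparisons, alpha or sample size. That stands, and it keeps the point modest.

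The classification is also less settled than the arithmetic suggests. The Data Review Committee determines global response under a charter that is not among the documents. SAP 3.7 counts a missing response as indeterminate in the denominator for analyses in mITT. SAP 3.2 otherwise uses reduced denominators where data are missing, unless specified. So these subjects might be dropped instead. However, SAP 2.2.1 defines the global cure denominator specifically, as everyone in the analysis population, and no passage takes these subjects out. Protocol 13.4.2 mentions an ITT analysis of global response, so use outside mITT was contemplated. But SAP 4.3.1.1 does not list that analysis, and no classification rule comes with it.

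Several stronger readings are tempting and are not supported:

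- A reader might infer that mortality is also undefined here. It is not: death from any cause by Day 30 can be determined whatever the culture result.
- A reader might infer that everyone outside mITT is uninfected. mITT requires Central Laboratory confirmation, while SAP 2.2.2 falls back on local mycology when central data are unavailable, so some may be classifiable. Subjects positive on a rapid test but culture-negative are not shown to be uninfected either.
- A reader might take 15% as the expected share of the PK Population. It is a share of randomized subjects and includes anyone never dosed, who is in neither population.
- A reader might infer a likely false exposure trend. The uneven split is an illustration, and its gap lies within sampling noise.

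Two discrepancies would also partly survive the change. Day 1 and Day 8 tables will still differ in case mix, because mITT subjects also die or stop before Day 8. Totals will still not match the primary results exactly, because only samples inside the time windows count.

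**Conclusion.** The point holds for global response. As written, the PK Population tables can include subjects who cannot meet the definition of cure, and this departs from Protocol 7.1.1. For all-cause mortality it is only an inconsistency with the mITT population in Table 2-1.

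The size is uncertain. A 70% mITT cure rate would read as anything from 70% (no such subjects) to 59% (17). The lower end assumes that all 17 planned non-mITT subjects are dosed and have measurable concentrations, that none is classifiable from local cultures, and that all stay in the denominator. The documents establish none of these, so 59% is a bound and not an expectation.

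The primary conclusions are not at risk. This is a small correction, worth making because it is clear and cheap.

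**What to change.** In SAP 4.6, for the two efficacy endpoints only, replace the reference to the PK Population with: *in rezafungin subjects in both the PK and mITT populations*. Keep the full PK Population for the concentration summaries and the TEAE tables.

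State which tertile cut-points apply. Keeping the PK Population cut-points lets the efficacy and TEAE tables line up, with slightly unequal efficacy groups. Re-cutting within the restricted set gives equal groups, but cut-points that differ slightly from those in the TEAE tables.

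The cost is one phrase and one population flag. The efficacy tables lose up to 17/109, or about 15%, of their subjects: about 31 per tertile (92/3) instead of 36 (109/3).
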